The active component of BSS with antimicrobial effects is bismuth, which is poorly absorbed and mostly remains in the GI tract while salicylate is systemically absorbed in the stomach (9). The mechanism of action of BSS in the prevention of TD is thought to be due to bismuth's intraluminal antimicrobial properties and a reduction in the number of bacteria (4, 6, 9, 10). In-vitro studies suggest that bismuth's action is bactericidal (6, 11), even at various levels of intestinal pH and against a wide range of organisms (11). The precise mechanisms of action include the binding of ingested bacteria and subsequent marking of these organisms to be killed by host defenses, rendering the bacteria unable to attach to receptor sites that are important for colonization and infection (11), degrading the bacterial cell wall, inhibiting ATP synthesis, and inhibiting the function of the plasma membrane (9). This inhibition may occur in as little as 0.5–24 hours (9). BSS may also inactivate bacterial toxins before attachment to the intestinal mucosa (12). Viruses may be inhibited by BSS; it may prevent viral invasion and deter replication through unknown mechanisms (4).

There is a current domestic and international focus on preventing the acquisition of drug-resistant enteric bacteria by high-risk groups, including travelers (13). International travelers are at increased risk for acquiring gut organisms containing AMR genes (especially after travel to Asia), developing TD, taking antibiotics, and requiring hospitalization (14, 15, 16, 17). Although carriage of organisms containing gut AMR genes may be transient in most travelers (15), it can persist for ≥1 year in over 10% of travelers, increasing the risk of transmission to household members and others (18). Avoiding the use of antibiotics while abroad is one way to lessen acquisition of antibiotic-resistant organisms (19). BSS treatment of adult outpatients with acute diarrhea has been found to reduce antimicrobial medication use in a high prevalence area (20). It is currently unknown whether BSS affects the acquisition of gut AMR genes while traveling abroad; however, given BSS' antimicrobial properties, stability in acidic conditions, and blockage of receptor sites to prevent colonization, it is possible that prophylactic BSS may indirectly prevent acquisition of AMR genes in international travelers by preventing intestinal colonization of ingested microbes. More research must be done to address this uncertainty.

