Includes the 7 days prior to departure in which the pre-travel questionnaire and a biologic (stool) specimen is collected, the full duration of travel, and through 10 days maximum post-return from travel, or until both the post-travel questionnaire and submission of the post-travel biologic (stool) specimen is complete (a maximum of 17 days post-travel)

Travel companion (group):

Two or more study participants with a common relation (friends, colleagues, or relatives) with the same itinerary, who anticipate performing the same activities during travel

Trip duration:

The number of days spent in country; excludes air travel time

Severe TD:

Hospitalization to an inpatient ward either during travel or after travel with a diagnosis of diarrhea

Acquisition of AMR gene(s):

The presence in a post-travel biologic (stool) specimen of one or more antimicrobial resistance gene(s) that were not present in a pre-travel biologic (stool) specimen from the same person, and which is known to confer antimicrobial resistance to one or more antimicrobial agents ("resistome")

Medication compliance:

Full = participant takes all scheduled doses according to directions

Good = If <15% of BSS or placebo doses were missed during travel

Fair = If 15–30% of BSS or placebo doses were missed during travel

Poor = If >30% of doses were missed during travel

Questionnaire compliance:

Full = participant completes all questionnaires

Good = participant completes >80% of all during travel questionnaires, AND
both the pre- and post-travel questionnaires

Fair = participant completes between 30–80% of all during travel
questionnaires, including AT LEAST the pre-travel questionnaire

Poor = participant completes <40% of all during travel questionnaires, and AT
LEAST the pre-travel questionnaire

Biologic (stool) specimen compliance:

Full = BOTH specimens collected and sent

Fair = ONLY one specimen collected and sent

Poor = No specimens collected and sent

Loss to follow-up:

Failure to complete the post-travel questionnaire after three attempts to contact the participant or if submission of the post-travel biologic specimen (stool) occurs more than 10 days after return from travel or is not submitted

Participant Inclusion Criteria

Willing participants must meet the inclusion criteria as outlined here:

1. Be ≥ 18 and <70 years of age at the time of enrollment

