Participants will be asked to submit a web-based post-travel questionnaire within 10 days after return from travel, submit a biologic (stool) specimen, and provide all daily questionnaires that were completed during travel. This will be submitted via a pre-paid envelope addressed to the study clinic that was given to the participant when enrolled.

Study personnel will make follow-up telephone calls on days 3, 5, 7, and 10 after return as needed to encourage that the post-travel questionnaire, paper questionnaires from during-travel, and biologic (stool) specimens are all submitted.

The web-based post-travel questionnaire will include questions on:

1. The development of symptoms of TD since returning from abroad, including duration of symptoms
2. New antibiotic or other medication use
3. Adverse events

4. Contact with healthcare facilities or providers
5. Changes to travel itinerary during travel

Table 2. Schedule of CLINIC events (primary and secondary objectives):

	Stages			
	Pre-travel consultation (baseline)	Pre-travel (≤ 7 days before departure)	During travel	Post-travel (≤ 10 days after return)
Screening Questionnaire	X			
Informed Consent	X			
Pre-travel Questionnaire*		X		
Follow-up call(s)		X		X [†]
During travel Questionnaires			X	
Post-travel Questionnaire				X
Adverse Events Reporting			X	X

*Study personnel will call the participant to complete a pre-travel questionnaire 7 days before departure and to ensure that answers to the questions on the screening questionnaire have not changed. Reminder calls will occur as per **APPENDIX G**. If the traveler is leaving exactly 7 days after the pre-travel consultation/enrollment visit, this questionnaire can be performed at the pre-travel consultation/enrollment visit.

[†]Study personnel will call the participant within 3 days of return from travel to remind participants to complete their web-based post-travel questionnaire, submit any paper during travel questionnaires, and collect and submit the post-travel biologic (stool) sample. Reminder calls will occur as per **APPENDIX G**.

Laboratory Instruments

All participants will collect and submit a fresh biologic (stool) sample in the 7 days before departure and within 10 days after return. Participants will be

provided all instructions and materials necessary to collect and submit these samples at enrollment. All biologic (stool) specimens will be submitted by mail, and participants will be given pre-paid shipping materials.

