Participants will be provided two OMNIgene gut kits at their pre-travel consultation/enrollment visit once enrolled (see Biologic [Stool] Specimen Data Collection and Testing). These kits will come with instructions on use, handling, and shipment.

In the event that participants are able to provide a stool sample while in clinic for their pre-travel consultation/enrollment visit or during a non-study post-travel follow-up sick visit within 10 days of return, these samples will be aliquoted by study personnel at The New York Center for Travel and Tropical Medicine in the following manner:

*First, the required quantity will be placed in the participant's OMNIgene gut kit (per manufacturer directions) to be sent to CDC's Clinical and Environmental Microbiology Branch for resistome testing. The remainder will be frozen, and sent to CDC for analysis at a later date (note: OMNIgene gut kit does not allow for culture - a see Biologic [Stool] Specimen Collection and Testing). Only those participants who happen to have a biologic (stool) specimen collection completed at the clinic will have their stool analyzed by culture; this is not a requirement for participation and no additional compensation above that previously described will be offered.

Table 3. Schedule of LABORATORY events (secondary objective)

(Events from Table 2 still apply to these participants)

	Stages		
	Pre-travel	During travel	Post-travel
Biologic (stool) sample	X		X
Laboratory testing of stool	X		X

Analytic tests

Questionnaires: Data from the questionnaires will be analyzed for statistical significance comparing intervention vs placebo groups.

Biologic (stool) specimens: A highly multiplexed PCR assay detecting over 500 different AMR genes will be used to test the DNA extracted from all biologic (stool) specimens that were placed in the OMNIgene gut kit (see Biologic (Stool) Specimen Collection and Testing). Results will be analyzed to determine if the participants acquire gut AMR genes (changes to the “resistome”) as a result of travel and whether or not that change varied with the bismuth subsalicylate treatment received. Additionally, stool bacteriologic culture will be performed on those specimens submitted in clinic.

Intervention

We propose the inclusion of two arms to test BSS against placebo:

1. BSS 4 tablets po bid (2.1 grams total)
2. Placebo 4 tablets po bid

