Dosing will begin on the flight prior to arrival in the destination and will cease once they return home. The study medications must be taken twice daily (a morning and an evening dose); with time zone changes, the first dose should be taken to ensure that no longer than 12 hours passes before a subsequent dose.

Before departure, participants will be provided, free of charge, all needed study medication for the duration of their trip. Participants will be encouraged to take all doses of their medication and appropriately document on their daily during travel questionnaires if a dose was missed or taken off schedule.

Outcomes

The outcomes of this study will include:

	Favorable Outcome	Non-favorable Outcome
Hypothesis 1: Prevention of TD	Prevention of TD in the intervention group	TD in the intervention group at a rate similar to placebo; intervention drug side effects; adverse events

Hypothesis 2: Acquisition of AMR genes	Reduced or no presence of travel-associated gut AMR genes in the intervention group	No reduction in the presence of travel-associated gut AMR genes in the intervention group
---	---	---

The participant's study period will end in the following circumstances:

1. The traveler meets criteria for removal (see Criteria for Removal from the Study)
2. The participant voluntarily withdraws from the study (see Procedures for Implementing and Documenting Informed Consent)
3. The participant completes all study activities and submits all study questionnaires and biologic (stool) specimens
4. The participant is lost to follow-up

The participants will be instructed at enrollment to stop the study medication for any of the following reasons (although they will still be instructed to answer their questionnaires and submit biologic [stool] specimens as scheduled):

1. Antibiotics or BSS (either provided by the study personnel for TD treatment, or taken as an over-the-counter remedy) are taken for TD or for another medical condition
2. Any severe adverse events as described, such as signs and symptoms of salicylism or neurotoxicity, occur
3. Hospitalization for any reason

Barring the reasons listed above, the study medication should be taken throughout the trip duration, even if diarrhea occurs, if possible.

Criteria for Removal from the Study

Participants will be removed from the study when any of the following criteria apply:

1. Do not complete the pre-travel questionnaire (see Definitions for compliance)
2. Loss to follow-up (see Definitions)

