The identity of all study participants will be protected. All questionnaires will be coded using study and group IDs and participants will each be given a unique study ID and group ID. The unique study ID will include a site letter designation of "T", year, and participant number (provided numerically from 1 to 10,000). For example, the unique identifier for the first participant would be: T2017-00001. The group ID will begin with "G" and group number (provided numerically from 1 to 10,000). Those participants who are travel companions and have identical itineraries to other participants in the study and anticipate performing the same activities, (including family and friends), are given the same group number. For example, the group ID for the first participant would be G-00001. If they have a companion traveling with them, that participant would also be G-00001.

The original completed screening questionnaires and any original completed paper daily travel forms will be housed at the clinic in a secure location and destroyed per institutional guidelines.

Biologic (stool) specimens submitted by the participant will be coded. Labels will be provided to the participants for labeling the specimens and will include the participant's unique study ID and group ID. Specimens will be sent to the CDC Clinical and Environmental Microbiology Branch by the Center for Travel and Tropical Medicine for testing and storage.

Labels will also be provided to participants for the paper copies of the during travel questionnaire to ensure confidentiality and to avoid mislabeling.

The database will be password-protected and only study personnel at New York Center for Travel and Tropical Medicine clinic will have access to the password (and thus patient identifiers). No study personnel from CDC will have access to participant identifying information. Identifying information will be stored in a secure, passcode

protected file on a password protected computer and server. This file will be destroyed upon completion of the study.

Information Management and Analysis Software

Data will be managed securely in REDCap.

SAS v9.4 will be used for analysis.

Data Entry, Editing and Management, and Data Storage

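### The post-travel stool has no minimum interval after the last BSS dose and no visible collection date, so the plan could not show whether fewer detected AMR genes reflect short-lived suppression or prevented acquisition

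*Combined protocol and SAP*

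**What the plan says.** **Dosing.** Under Intervention: "Dosing will begin on the flight prior to arrival in the destination and will cease once they return home". There is no interval between the last dose and the earliest permitted stool.

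**Stool window.** Under Laboratory Instruments: "All participants will collect and submit a fresh biologic (stool) sample in the 7 days before departure and within 10 days after return". Procedures and inclusion criterion 7 give the same 10 days, and none of these sets an earliest day. The loss-to-follow-up definition turns on the day of mailing, applying where "submission of the post-travel biologic specimen (stool) occurs more than 10 days after return from travel". The study-period definition in the same section allows up to 17 days after travel for the specimen to be submitted.

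**Sick visits.** Laboratory Instruments and Biologic (Stool) Specimen Collection and Testing allow a stool given "during a non-study post-travel follow-up sick visit within 10 days of return". That stool fills the resistome kit before anything is frozen or cultured.

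**Endpoint.** Definitions counts a gene as acquired if it is in the post-travel stool and was not in the pre-travel stool. There is no time element. Appendix I, Table 3, tabulates acquisition gene by gene, with no row or column for timing.

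**Dates.** Provision for Protecting Privacy/Confidentiality: "Labels will be provided to the participants for labeling the specimens and will include the participant's unique study ID and group ID". Appendix E asks for neither the return date nor a stool date. Appendix D does record the calendar date and tablets taken each day, from day 1 (arrival in country) to day 21.

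**Biology.** Current State of Knowledge says of bismuth "which is poorly absorbed and mostly remains in the GI tract", and of resistance carriage: "Although carriage of organisms containing gut AMR genes may be transient in most travelers". Study Limitations discusses neither in relation to stool timing.

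**The concern.** A stool passed on the day of return may come from a gut that still contains bismuth; a stool from day 9 or 10 shows what has persisted without it. The first situation arises only in the BSS arm, so randomization does not remove it. If bismuth temporarily lowers the number of detectable genes, the BSS arm would show fewer acquired genes even if colonization during travel was the same in both arms. The Outcomes table would count this as favorable, since it asks only for reduced presence of travel-associated genes.

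The distinction matters because of the stated use of the results. Under Intended Potential Use of Study Findings, the trial is meant to support advice that protects the non-traveling public from imported resistance. That depends on what travelers still carry once the drug has gone.

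The sick-visit route adds a second problem. Participants are seen after travel only if they are ill. Illness therefore decides who is sampled at a clinic visit and when, and the trial expects illness to differ by arm.

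**Working it through.** **1. The plan's own figure.** The only sample size is for TD: 40% versus 28%, alpha 0.05 (two-sided reproduces it), 80% power. With a mean proportion of 0.34, n per arm = [1.96√(2×0.34×0.66) + 0.8416√(0.40×0.60 + 0.28×0.72)]² / 0.12² = (1.313 + 0.559)² / 0.0144 ≈ 243.5, so 244 per arm and 488 in total. It reproduces and is not in question. No sample size is given for the AMR endpoint. Budget Table 5 costs testing for 250 participants, or 125 per arm if split equally, so both sizes are shown below.

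**2. Residual suppression with no true effect.** Let p be true acquisition in both arms, f the share of BSS stools taken while detection is reduced, and s the relative reduction. Observed BSS rate = p(1 − fs), so apparent RR = 1 − fs. The documents give none of these inputs. With p = 0.50 and f = 0.50 assumed:

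| s | BSS rate seen | Apparent RR | Significant for BSS, 244 per arm | Same, 125 per arm |
|---|---|---|---|---|
| 10% | 47.5% | 0.95 | 8% | 6% |
| 30% | 42.5% | 0.85 | 38% | 22% |
| 50% | 37.5% | 0.75 | 80% | 51% |

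The nominal rate in that direction is 2.5%. With f from 25% to 75% and s from 10% to 50%, the apparent RR runs from 1 − 0.025 = 0.975 to 1 − 0.375 = 0.625. If s is zero, there is no bias at all.

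**3. Transient carriage.** Assume exponential loss with half-life H. Carriage left at day 10 is 2^(−10/H): 37%, 61% and 79% for H = 7, 14 and 30 days. If both arms are sampled on the same days, this lowers detection equally and costs power only. If the BSS arm were sampled on average 2 days later, the spurious RR would be 2^(−2/H): 0.82, 0.91 and 0.95. Bias therefore needs a difference in timing between arms.

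**4. Would a date and simple adjustment be enough?** Take the last row of the table at 244 per arm, with half the stools early in both arms and suppression only in early BSS stools. In simulation under no true effect, the arm comparison was significant in about 80% of trials, both unadjusted and after adding a main effect for the interval since the last dose. A main effect cannot absorb something present in one arm only. With an arm-by-interval term, the arm effect in later stools was significant in about 5%.

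**5. Power of the interaction test.** In that case (122 stools per cell; 50% in three cells, 25% in the fourth) the interaction is a log odds ratio of ln(1/3) = −1.10. Its SE = √(3/(122×0.25) + 1/(122×0.1875)) = 0.377. So z = 2.91 and power is about Φ(2.91 − 1.96) = 83%. With s = 30% (early BSS cell 35%), the log odds ratio is −0.62, SE 0.367, z = 1.69 and power about 39%. At 125 per arm, s = 50% gives SE 0.527, z = 2.09 and power about 55%. The analysis can reveal a large effect, but cannot rule out a moderate one.

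**The case against.** The strongest reply is that suppression is a hypothesis. The assay is PCR on extracted DNA, which does not depend on culture, so killing bacteria does not by itself remove the gene signal. The documents give no clearance time for bismuth. A reader might infer one from the 0.5 to 24 hours in Current State of Knowledge, but that is how quickly inhibition may occur and says nothing about how long it lasts after the last dose. This stands: the mechanism is plausible on the protocol's own account, but its size is unknown.

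Four further inferences are tempting and not supported.

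- **That no collection date is captured anywhere.** Appendix K and the kit instructions are not in the text, and the label sentence sits in a privacy section and need not be a full specification. Only the absence from the visible forms, label description and table shells can be asserted.
- **That the last dose cannot be dated.** Appendix D dates the doses, and a sick-visit stool has a known visit day. The gaps are the home stool date and doses on the way home: Appendix D ends at day 21, and trip duration excludes air travel.
- **That the window is judged on mailing alone.** Procedures states the 10 days for collection; the loss-to-follow-up rule states it for submission.
- **That transient carriage is itself a bias between arms.** With timing balanced by randomization it is not. Sick visits are one route to imbalance, but the protocol expects most stools to be self-collected.

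What survives is that one stool, taken at an uncontrolled and visibly unrecorded interval after the drug, cannot answer the question if suppression occurs.

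**Conclusion.** The point holds as a cheap improvement to the secondary objective. The TD objective and its sample size are untouched. The plan accepts one post-travel stool from return to day 10, sets no minimum interval after the last dose, lets a sick-visit stool serve as the resistome specimen, and has no visible provision for dating home stools or analyzing by timing. If residual bismuth lowers detection, the effect falls on the BSS arm only and the planned comparison would not expose it.

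The 8% to 80% in the working is not a predicted false-positive rate. It rests wholly on assumed acquisition, early share and suppression, and serves only to show that suppression of 30% to 50% in half the BSS stools would be enough to matter. A reader might conclude that a lower AMR rate in the BSS arm would be an artifact. The documents do not support that; they support only that the two explanations could not be separated.

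**What to change.** 1. **Dates.** Record the collection date of each stool on the label or in Appendix E, and the return date in Appendix E. Take the last-dose date from the daily questionnaire, adding a line for doses on the way home. Judge the window on collection date, and reconcile the 10-day and 17-day limits in Definitions.

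2. **Analysis.** Pre-specify, as a sensitivity analysis, the AMR comparison with an arm-by-interval term or stratified by days since return. A main effect for days since last dose is not enough. Define strata by days since return: a cut on days since last dose would automatically retain participants who stopped study drug early after antibiotics, BSS treatment or hospitalization, a selection linked to illness and to AMR. State in the report that dates can reveal suppression but cannot fully separate it from prevention.

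3. **Sick-visit stools.** Keep the home kit for the resistome specimen and use sick-visit stool for culture and storage. Failing that, flag sick-visit stools and repeat the comparison without them.

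A fixed start at day 3 should not be imposed. No clearance time supports it, and it would shorten the time available under a rule that treats late submission as loss to follow-up.

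Cost: a few date fields, one or two extra analyses of limited power, and possibly a few lost specimens. No additional stool is needed.
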